Secondary Objective(s) and/or Endpoint(s)	The secondary objectives are to determine the capability of the FlowMet-R in prognosis of requiring vascular intervention or amputation within three and six months following the initial visit. Additionally, to investigate the correlation between FlowMet-R measurements and peripheral artery stenosis. Finally, to assess the correlation between changes in ABI/TBI/Rutherford Classification and changes in FlowMet-R data between any two time points.
Study Design	Multi-center, non-randomized, longitudinal study with three and six month follow-up.
Sample Size	PAD Cohort: Cohort will consist of 240 limbs with PAD including a minimum of 54 limbs with claudication and a minimum of 100 limbs with CLI. All comers - any patient scheduled for peripheral vascular

	
assessment who is not subject to exclusion may be approached for enrollment in the disease positive arm. Exclusion criteria are detailed in Section 8.4. This will include patients in the registry who have a planned endovascular or surgical intervention to address their PAD.
 
Healthy Cohort: Cohort will consist of 160 control limbs. Any patient over 40 years old and without suspected PAD may be approached for enrollment in the healthy control arm. Healthy subjects may be enrolled from other departments within the clinic/hospital, can be from the local community, or can be actively recruited for participation (such as researchmatch.com or active volunteers).
 
Registry: Patients diagnosed with PAD at baseline procedure who are scheduled to undergo an endovascular treatment of the lower limbs will be included in the registry data for this study. The registry will be established to record FlowMet-R measurements, angiographic films, and any additional relevant information immediately prior to, during, and immediately following peripheral vascular interventional procedures for enrolled patients.

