3.1	MAJOR CHANGES			
	Migration to Medtronic Template	Acquisition of LAS by MDT complete	Informed Consent Form	
	Changed FlowMet assessment procedure to implement the standard of care rest period for ABI/TBI instead of FlowMet-specific 5 minute rest period. The same rest period may be applied for FlowMet and ABI/TBI measurements.	Changed to ensure sites can follow their own specific standard of care for ABI/TBI.		
	Created a health-cohort specific procedures flowchart.	Improved readability		
	Added exclusion of PAD cohort: 
 – Subject may not have revascularization surgery within the last 90 day – Subject cannot lay safely in supine position 	Added language to avoid ambiguity in patient symptoms and to avoid putting patient in supine position who may not be able to safely be supine for required length of time.		
	Added exclusion of Healthy cohort 
 – Subject does not have suitable finger or toes to attach the probe – Subject is under 40 years old 	Added for clarity and to ensure healthy cohort maintains an age-matched population with PAD cohort.		

FlowMet-R Blood Flow Measurement for PAD and CLI Clinical Investigation Plan

Version 3.1

Page 41 of 42

Form

Medtronic

	Changed FlowMet assessment procedure to note that if 5 or more repeated attempts are made with poor-quality data, then the clinician will choose the optimal record to the best of their knowledge.	Added to ensure procedure was in place for the rare occurrence where FlowMet readings cannot accurately be obtained after 5 attempts.		
	Changed date requirements of ultrasound or angiographic imaging from within 24 hours to 30 days.	Loosened this restriction to improve patient enrollment. This restriction was determined able to be reduced because very little change is expected to occur in the stenosis % in chronic PAD patients over the prior 30 days before their imaging exam. Additionally, 30 days is a commonly accepted timeframe for validity of stenosis imaging tests used in similar PAD studies.		
MINOR CHANGES				
	Created separate event schedule C specifically for healthy cohort.	Additional language added for readability.		
	Specified patients enrolled in PAD cohort cannot be grouped into healthy cohort, even after their PAD is treated.	Always intended this way but provided additional language for clarity.		

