4.1.2.1 Secondary Endpoints

- Utilize FlowMet-R data to create a predictive model for the prognosis of vascular intervention within a three and six month timeframe from initial visit.
- Employ the predictive model of PAD severity to generate an ROC curve for diagnosis of significant stenosis (>50%) in the iliac, femoral, popliteal, peroneal, or tibial arteries.
- Conduct a correlation test between the predictive model of PAD severity and greatest percent stenosis in the iliac, femoral, popliteal, peroneal, or tibial arteries.
- Conduct a correlation test between changes in the predictive model of PAD severity and corresponding changes in ABI, TBI, and Rutherford Classification between any two study time points.

5. Investigation Plan

This study is a non-randomized, multi-center, longitudinal study of healthy subjects and subjects with PAD who are scheduled for ABI, TBI, and either Duplex ultrasound or Angiographic assessments in a vascular clinic. Subjects will first be evaluated for study inclusion/exclusion. If the subject meets the inclusion criteria and wishes to enroll in the study, they will be asked to sign an informed consent form (ICF) and considered for enrollment. If the subject meets inclusion criteria and is enrolled, the subject will undergo approximately 3 minutes of FlowMet-R blood flow measurements in addition to their routine standard of care examination.

Subjects enrolled in the PAD cohort will be assessed according to Event Schedule A in the clinical investigation protocol (CIP) at approximately 0, 3 months, and 6 months. Subject follow ups must meet the scheduled time window within +/- 30 days. Subjects that require a vascular (re)intervention for PAD-related treatment before the final measurement (6 month follow up) will have pertinent data collected and saved in the study registry. The vascular procedure may change the timing with respect to the amount of months after baseline that the follow up visits occur. In that case, the standard of care follow up visits post intervention will be adhered to, and data will be collected from the follow up visits that correspond most closely to timepoints at 3 and/or 6 months post baseline visit.

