5.6 Exclusion Criteria

Candidates for this study who meet any of the following criteria at the time of the baseline visit are not eligible to be enrolled in this study:

PAD Positive Cohort Exclusion

- Subject is under 40 or unable to consent.
- Subject has any medical condition, which, in the judgment of the Investigator and/or designee, makes the subject a poor candidate for the investigational study.
- Subject is excluded from analysis if no stenosis is found during Doppler but Tibial disease is suspected and Tibial ultrasound is not able to be performed.
- Subject does not have a suitable finger to attach the FlowMet-R probe.
- Subject does not have a suitable 1st or 2nd digit to attach FlowMet-R probe on the limb of interest.
- Subject has undergone revascularization within the last 90 days
- Subject cannot lay safely in a supine position.

Healthy Cohort Exclusion

- Subject is under 40 or unable to consent.
- Subject has any medical condition, which, in the judgment of the Investigator and/or designee, makes the subject a poor candidate for the investigational study.
- One or more limbs has a prior or current diagnosis of PAD, or is reasonably suspected of having a diagnosis of PAD.
- Subject does not have a suitable finger to attach the FlowMet-R probe.
- Subject does not have a suitable 1st or 2nd digit to attach FlowMet-R probe.
- Subject has undergone revascularization within the last 90 days

6. Determination of Sample Size

The rate of PAD and CLI within the population seen at a typical vascular clinic is estimated from a prior investigation. In that study, 100 limbs were assessed using the ABI and graded using the Rutherford classification scheme. PAD (diagnosed via ABI score of <0.9) was present in 63% of limbs. CLI (estimated as having a Rutherford category of ≥ 4) occurred in 15% of limbs. FlowMet-R data was also collected from the above limbs, and the data analysis techniques used in the data analysis section below were applied to build a diagnostic model for PAD and CLI. ROC curves were then generated for the diagnosis of both Claudication and CLI. The resulting area under the curve (AUC) for these ROC curves was 0.67 and 0.80, respectively. However, the Claudicant group AUC had a tighter confidence interval due to larger sample size (84 vs. 22, respectively).

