7.1.3 Analysis Sets

Full Analysis Set

The full analysis set will include all participants and be used for all analyses. Visits outside of visit windows will be assigned to the nearest window. If a participant is missing data for a specific analysis, they will be excluded for that analysis. Within the analysis set, the grouping participants into the healthy, PAD (definitions 1 and 2), and CLI groups are defined in section 4.1.1.1.

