7.10 Evaluation of Objectives

7.10.1 Primary Objectives

The primary objectives will compare the 95% CI of the AUC from the ROC curve to a value of 0.5 at 0-, 3-, and 6-months for the two definitions of PAD and one definition of CLI using the acceleration time from the FlowMet-R device. The 95% CI will not be corrected for repeated measures within a participant. If the 95% CI of the AUC excludes 0.5 at all time points for PAD or CLI, the acceleration time from the FlowMet-R device will be considered predictive of the respective endpoint. The 95% CI of the AUC will be derived using the method described in DeLong, et al (1998) [15]. Note, the definition of PAD will be defined two ways and analyzed separately. Definitions of PAD and CLI are provided in Section 4.1.1.1.1.

Three supplementary summaries will be computed. The sensitivity and specificity will be computed by selecting the point on the ROC curve closest to the upper left corner. Accuracy will be computed as the number of limbs correctly diagnosed divided by the total number of limbs.

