7.10.2 Secondary Objectives

The secondary endpoints will be analyzed as follows:

1. The capability of the acceleration time from the FlowMet-R device to predict a vascular intervention or amputation will occur within three and six months following initial visit will be determined using the AUC from an ROC curve where the endpoint is vascular intervention or amputation within 7 months, which is the end of the 6 month follow-up window. The 95% CI of the AUC will be derived using the method described in DeLong, et al (1998) [15].
2. The capability of the acceleration time from the FlowMet-R device to predict a $\geq 50\%$ stenosis determined using the AUC from an ROC curve where the endpoint is vascular intervention or amputation within 7 months, which is the end of the 6 month follow-up window. The 95% CI of the AUC will be derived using the method described in DeLong, et al (1998) [15].
3. The correlations between the acceleration time from the FlowMet-R device and peripheral artery stenosis, changes in ABI, and changes in TBI will be computed using Pearson correlations. The changes for ABI and TBI will be as follows: 0 to 3 months, 0 to 6 months, and 3 to 6 months.
4. The correlation between the acceleration time from the FlowMet-R device and changes in Rutherford Classification will be computed using the Spearman correlation. The changes for Rutherford Classification will be as follows: 0 to 3 months, 0 to 6 months, and 3 to 6 months.

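### The change correlations in SAP 7.10.2 items 3-4 pool limbs revascularised during the interval with untreated limbs, so a shared shift after treatment can look like tracking.

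*SAP*

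**What the plan says.** - **Who is enrolled.** The protocol synopsis (Sample Size) says of the PAD cohort: "This will include patients in the registry who have a planned endovascular or surgical intervention to address their PAD". The synopsis keeps the registry open until at least 25 interventional procedures have been captured.
- **What happens after a procedure.** SAP section 5: "Subjects that require a vascular (re)intervention for PAD-related treatment before the final measurement (6 month follow up) will have pertinent data collected and saved". It adds that, for these subjects, "data will be collected from the follow up visits that correspond most closely to timepoints at 3 and/or 6 months post baseline visit". Revascularisation is not among the exit reasons in protocol 9.10.
- **Analysis set.** SAP 7.1.3: "The full analysis set will include all participants and be used for all analyses".
- **Change correlations.** SAP 7.10.2 items 3 (Pearson; ABI and TBI) and 4 (Spearman; Rutherford) use three intervals. For ABI and TBI: "The changes for ABI and TBI will be as follows: 0 to 3 months, 0 to 6 months, and 3 to 6 months". Neither item has a stratum, covariate, exclusion or sensitivity analysis for revascularisation in the interval.
- **Which quantity is correlated.** The endpoint in SAP 4.1.2.1 sets change in the predictive model against change in ABI, TBI or Rutherford class. Items 3-4 as worded set acceleration time itself, not its change, against those changes.
- **Follow-up ROC curves.** SAP 7.10.1 has the same pooling at months 3 and 6, under a rule that begins "If the 95% CI of the AUC excludes 0.5 at all time points for PAD or CLI".

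**The concern.** Revascularisation is meant to change limb perfusion. Limbs treated within an interval may therefore move together on ABI, TBI and the FlowMet-R measure, while untreated limbs may change little. One correlation over both groups then combines two things: both measures shifted after treatment, and one measure follows the other from limb to limb. A reader of the pooled coefficient cannot tell these apart.

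The distinction matters because SAP 5.2 presents the device as a simple and continuous way of assessing PAD severity. A pooled correlation could be read as evidence that it follows gradual change in limbs nobody has treated, when all of the association came from the treated ones.

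**Working it through.** The plan states no expected correlation, and its sample-size section deals only with AUCs, so there is no plan figure to reproduce.

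**Inputs from the documents.** 240 PAD limbs (SAP section 6). At least 25 procedures (protocol synopsis), which is 25/240 = 10.4% of PAD limbs if each procedure is on a different one. This is a floor; no expected rate or maximum is given.

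**Assumptions.** A share p of limbs is treated in the interval. Treated limbs shift by k within-group SDs on both measures, scored so that improvement has the same sign on each. Correlation is zero within the treated and within the untreated group. Limbs are independent and none is lost. Both p and k are assumed.

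**Formula.** With unit within-group variance, the between-group covariance is v = p(1 − p)k² and each total variance is 1 + v. So pooled r = v/(1 + v).

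| p | k | v | pooled r | chance of a significant r at 240 limbs |
|---|---|---|---|---|
| 10.4% | 1 | 0.093 | 0.09 | 0.26 |
| 20% | 1 | 0.160 | 0.14 | 0.57 |
| 30% | 1 | 0.210 | 0.17 | 0.77 |
| 30% | 1.5 | 0.4725 | 0.32 | about 1.00 |
| 30% | 2 | 0.840 | 0.46 | about 1.00 |

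With a 0.5 SD shift, r is only 0.02 at 10.4% treated and 0.05 at 30%.

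**Interval for r = 0.32.** Fisher z = 0.333, standard error 1/√237 = 0.065, limits 0.333 ± 0.127, giving a 95% CI of about 0.20 to 0.43. Correlated limbs or lost visits would widen it.

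Within each stratum r is zero by construction, so separate reporting removes the artefact. The formula is for Pearson correlations of change with change. The mechanism also reaches the Spearman correlation in item 4, but these values were not derived for it.

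**Follow-up AUCs.** The direction here is not fixed.

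- *Upward.* Suppose AUC is 0.5 within treated and within untreated limbs, p = 30%, k = 1, and 60% of treated but 10% of untreated limbs become PAD negative (assumed rates). Negatives are 0.18 + 0.07 = 25% of limbs. The treated share is 0.18/0.25 = 0.72 of negatives and 0.12/0.75 = 0.16 of positives. Pooled AUC = 0.5 + (Φ(1/√2) − 0.5)(0.72 × 0.84 − 0.28 × 0.16) = 0.5 + 0.260 × 0.56 = 0.646 (95% CI 0.570 to 0.722). At 10.4% treated it is 0.594 (0.499 to 0.689).
- *Downward.* Suppose the true AUC is 0.80, and 30% of positives are treated limbs whose flow has improved by 1 SD while their label has not changed. The separation for AUC 0.80 is 1.19 SD, so the treated positives have AUC Φ(0.19/√2) = 0.55. Pooled AUC = 0.7 × 0.80 + 0.3 × 0.55 = 0.73.

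**The case against.** The strongest reply is that response to revascularisation is a legitimate signal. The endpoint asks about change between any two time points, and a device that moves with ABI and TBI after treatment has registered a real change. Stratifying removes the main source of true change, and untreated limbs have a narrow range in which to show tracking. This stands. It is why the pooled value should be kept and why an adjusted (partial) correlation is not asked for. It does not make the pooled value evidence about untreated limbs.

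It is also fair that zero within-group correlation is an extreme case, that the effect is small at the only documented count, and that SAP 7.2 calls the objectives descriptive, with no success criterion for items 3-4. These points limit the size and weight of the problem; they do not remove it.

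Three stronger readings are tempting, and the documents do not support them.

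- *That the entry rule already bars these limbs.* SAP 5.6 excludes at baseline when "Subject has undergone revascularization within the last 90 days". The rule applies to subjects, at entry, for recent treatment only. If procedures are spread evenly after baseline, 90/91 = 99% fall within 90 days of a day-91 visit, but 90/122 = 74% at day 122 and 90/183 = 49% at day 183.
- *That the sponsor regards month-3 labels as ambiguous.* The protocol version history says "Added language to avoid ambiguity in patient symptoms", but that justifies an eligibility criterion. The same log and the current text deliberately use post-procedure visits.
- *That pooling could by itself produce primary success.* Each visit's label comes from that visit's own ABI and TBI, limbs that improve are deliberately counted as PAD negative, and the rule also requires success at baseline, where recently treated subjects are excluded.

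**Conclusion.** The point holds for the change correlations. The documents keep limbs revascularised in the interval in the analysis, enrol patients with planned procedures, and specify nothing to separate the two groups. Under the stated assumptions, pooling alone gives r of about 0.09 at the 25-procedure floor with a 1 SD shift, 0.17 at 30% treated with 1 SD, and 0.32 at 30% with 1.5 SD. Actual size depends on the share treated and the shift, neither of which is documented, so it may be negligible or material.

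For the follow-up AUCs the same pooling is a reason for a supportive check only. Its effect could go either way, and the documents do not show that the success rule in 7.10.1 is undermined.

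**What to change.** In SAP 7.10.2 items 3-4:

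1. State that both sides are changes over the same interval, to agree with the endpoint in 4.1.2.1.
2. Keep the pooled coefficient. Beside it, report each change correlation, with its 95% CI and number of limbs, separately for limbs with and without revascularisation in that interval. State how a limb treated before month 3 is classed for the 3-to-6-month interval.
3. State that any claim of tracking in untreated limbs rests on the untreated stratum alone.

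In SAP 7.10.1, leave the success rule unchanged and add, as supportive sensitivity analyses, the month-3 and month-6 AUCs without limbs revascularised since baseline.

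The cost is SAP wording and extra tables, settled before the data are analysed. Item 1 of 7.10.2 already needs the timing of interventions. Because the registry may close once its target is met, treated limb and procedure date should not be taken from the registry alone. Stratum estimates will be less precise than the pooled one, and a low correlation in untreated limbs may partly reflect restricted range. The sensitivity AUCs may lose many PAD-negative limbs, because healthy subjects have a single visit and follow-up negatives can come only from subjects enrolled in the PAD cohort. The report should give these counts.

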7.11 Safety Evaluation

A listing of any site-reported Adverse Events (AEs) including Serious Adverse Events (SAEs), will be created if any are observed in the study. The listing will include the AE description, AE start and end dates, relationship to the device, whether the AE is resolved, and whether the AE was considered an SAE..

A table of all observed device deficiencies that could have led to a serious adverse device effect will be created if any are observed.

A listing of all deaths and the reason for death will be created if any are observed.

7.12 Changes to Planned Analysis

Patients will be classified based on definitions in Section 4.1.1.1.1 no matter the cohort they were originally enrolled in for the study.

8. Validation Requirements

To ensure the quality of the statistical results and datasets created for the study, the following validation requirements will be implemented. Programs that contribute directly or indirectly to the results pertaining to the primary and secondary objectives including TLG (Tables, Listings, and Graphs) development will be validated at least at level II by a statistician or a statistical programmer. Level I validation consists of a statistician or statistical programmer reviewer who independently programs output and then compares the output with that generated by the original statistician or statistical programmer according to the current work instruction. Level II: The peer reviewer reviews the code; where appropriate, performs manual calculations or simple programming checks to verify the output. Level III validation may be used for any previously validated program where only minor/administrative changes were made (e.g., change the location of the data directory). For level III validation, the original statistician or statistical programmer performs a visual inspection of the code and output to confirm functionality according to the current work instruction. Any results that are used for external publication or reports should be validated at levels I.

9. References

1. Mosely, L.H. and F. Finseth, Cigarette smoking: impairment of digital blood flow and wound healing in the hand. *The Hand*, 1977(2): p. 97-101.
2. Stadelmann, W.K., A.G. Digenis, and G.R. Tobin, Impediments to wound healing. *The American journal of surgery*, 1998. 176(2): p. 39S-47S.
3. Cronberg, C., et al., Peripheral arterial disease. *Acta Radiologica*, 2003. 44(1): p. 59-66.
4. Ouriel, K., Peripheral arterial disease. *The lancet*, 2001. 358(9289): p. 1257-1264.
5. Falanga, V., Wound healing and its impairment in the diabetic foot. *The lancet*, 2005. 366(9498): p. 1736-1743.
6. Norgren, L., et al., Inter-society consensus for the management of peripheral arterial disease (TASC II). *European Journal of Vascular and Endovascular Surgery*, 2007. 33(1): p. S1-S75.

